Obtain informed consent	X																				
Inclusion/exclusion criteria	X	X	X																		
Demographics	X																				
Psoriasis/PsA medical history / previous therapies	X																				
Relevant medical history/current medical conditions	X																				
Washout evaluation/instruction	X																				
PsA CASPAR criteria		X																			
Smoking and alcohol history			X																		
Cardiovascular medical history	X																				
Physical Exam ⁴		X	X	X	X	X	X	X	X	X	X	X	X	X	X	X	X	X	X		
Height		X																			

[figure not shown]

Weight		X	X							X									X			
Vital signs		X	X	X	X	X	X	X	X	X	X	X	X	X	X	X	X	X	X	X		X
Chest X-ray ⁵		X																				
ECG		X																				
Prior/Concomitant medication/ non-drug therapy	X	X	X	X	X	X	X	X	X	X	X	X	X	X	X	X	X	X	X	X		X
Randomization via IRT			X																			
Administration of sc study treatment via PFS at study site			X	X	X	X	X	X	X	X	X	X	X	X	X	X	X	X	X			
Adverse Events/SAEs ³ (incl. injection site reaction & occurrence of infections)	X	X	X	X	X	X	X	X	X	X	X	X	X	X	X	X	X	X	X	X	X	X
QuantIFERON TB-Gold test		X																				
Hematology, blood chemistry ⁶		X	X						X	X			X				X			X		
Serum pregnancy test		X																				
Urinalysis/Urine pregnancy test ⁷			X				X		X	X		X		X		X			X			
Anti-CCP	X																					
Rheumatoid factor (RF)	X																					
High sensitivity C-Reactive protein (hsCRP)		X	X	X			X	X	X	X	X	X	X	X	X	X	X	X	X	X		
Erythrocyte Sedimentation Rate (ESR) ⁷		X	X	X			X	X	X	X	X	X	X	X	X	X	X	X	X	X		
Tender and swollen joint		X	X	X			X	X	X	X	X	X	X	X	X	X	X	X	X	X		

Responder Status Assessment ⁹										X	X	X	X	X	X	X	X	X		
Treatment period 1 completion form										X										
Treatment period 2 completion form																		X		

¹ If washout period is ≤ 4 weeks, visit 1 & visit 2 can be performed the same day
² Patients who discontinued prematurely or withdrawn during a specific treatment period should return for a final visit. The final visit should be scheduled approximately four (4) weeks after the last study treatment, and should be performed before any new treatment is initiated
³ AEs/SAEs occurring after informed consent has been obtained must be reported. Patients who **discontinued prematurely** should be contacted **via telephone** to collect AE/SAEs information. Any AE/SAEs that occur in the following 84 days (12 weeks) after last dose of study drug must be reported.

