1.1 Study design

This study uses a multicenter, randomized, double-blind, placebo-controlled, parallel-group design. Approximately 250 adult patients (in 2:2:1 ratio; 100 secukinumab 300 mg, 100 secukinumab 150 mg and 50 placebo) with active psoriatic arthritis (PsA) and with a target skin lesion with PASI score of 1 or greater will be randomized from approximately 65 investigative sites in the United States.

Screening will be flexible in duration based on the time required to wash out prior antirheumatic medications and have a duration of up to 8 weeks before randomization, followed by a treatment period up to Week 52.

Patients that do not require a washout, can proceed on to the baseline visit once all inclusion/exclusion criteria are being met.

At baseline (BL), patients whose eligibility is confirmed will be randomized to one of three treatment groups and will enter the Placebo-Controlled Treatment Period.

Treatment Period 1

The Treatment Period 1 is defined as starting from Randomization through Week 16 (prior to the Week 16 dose). At the start of the Placebo-Controlled Treatment Period, patients will be randomized via IRT in a 2:2:1 ratio to one of three treatment groups (secukinumab 300 mg s.c., secukinumab 150 mg s.c. or placebo s.c.).

- **Group 1- Secukinumab 300 mg**: secukinumab 300 mg (two s.c. injections of the 150 mg dose) once weekly for five weeks (at Baseline, Weeks 1, 2, 3, and 4), followed by dosing every four weeks.
- **Group 2- Secukinumab 150 mg**: secukinumab 150 mg (one s.c. injection of the 150 mg dose and one s.c. secukinumab injection of placebo) once weekly for five weeks (at Baseline, Weeks 1, 2, 3, and 4), followed by dosing every four weeks.

• **Group 3- Placebo**: placebo (two s.c. injection of 150 mg secukinumab placebo per dose) once per week for five weeks (at Baseline, Weeks 1, 2, 3, and 4), followed by dosing every four weeks.

Treatment Period 2

- Patients receiving secukinumab 300 mg (**Group 1**) will continue to receive same dose up to Week 52.
- At Weeks 16, 28 and 40 patients on secukinumab 150 mg (**Group 2**) will be classified as responders (≥ 20% improvement from BL in both tender and swollen joint counts) or non-responders.
 - At Weeks 16, 28 and 40 patients on secukinumab 150 mg (Group 2) who are responders will continue to receive secukinumab 150 mg (1.0 mL) plus placebo (1.0 mL) every 4 weeks until next evaluation of responder status at weeks 28 or 40.

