2.1 Data analysis general information

Data will be analyzed by Novartis Product Life-Cycle Services and/or a designated Contract Research Organization.

It is planned that the data from all centers that participate in this protocol will be combined, so that an adequate number of patients will be available for analysis. Analysis datasets and statistical outputs will be produced using the most recent SAS[®] Version 9.4 (SAS Institute Inc., Cary, NC, USA), and stored in Novartis global programming & statistical environment (GPS).

As the primary analysis time point is Week 16, there will be a database lock after all patients have completed the Week 16 visit and data are clean and complete. At that time, only the statistician and programmer(s) from Novartis and/or a designated CRO will be unblinded in order to perform the analysis. Results from the analyses of all data through Week 16 will be shared internally. For publication purposes, summary results from the Week 16 primary analysis time point may be shared with the health care community; however, individual subject-level data will remain blinded until the end of the trial. A final database lock will occur when all patients have completed the study.

Summary statistics for continuous variables will include mean, standard deviation, standard error of mean, median, 25th and 75th percentiles, interquartile range, minimum, and maximum at each time point. Summary statistics for discrete variables will be presented in the number and percent of patients in each category. Summary statistics will also be presented graphically wherever applicable. If not otherwise specified, p-values and confidence interval (CI) will be presented as two-sided and the default level of significance will be set to 0.05 (two-sided). For all continuous variables (efficacy and safety), change from baseline and percentage change from baseline by visit will also be presented.

Data analyses will be presented by treatment group. Efficacy and safety data for the placebocontrolled period (or the entire Treatment Period as appropriate) will be presented by the following 3 treatment groups. Patients may be included in more than one treatment group for some analyses (e.g. exposure-adjusted adverse events over the entire treatment period).

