5.4.6 Mixed-effects repeated measures model

Change from baseline in log (hsCRP) will be analyzed using mixed-effects model repeated measures (MMRM) with treatment (3 treatment groups), visit, baseline hsCRP, methotrexate usage at baseline (yes, no), and body weight (kg) as explanatory variables. An unstructured covariance structure will be assumed for this model.

SAS code for mixed model:

proc mixed data=aaa; class TRT USUBJID AVISITN; model CHG=TRT AVISITN WEIGHT BASE / s ddfm=kr; lsmeans TRT*AVISITN / diff cl; repeated AVISITN / type=un subject=USUBJID; run;

In case the MMRM model does not converge the following sequential steps will be used: 1. change ddfm=kr to ddfm=bw. If still no convergence, perform step 2.

2. change type=un to type=cs.

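### The non-convergence fallback for the log(hsCRP) repeated-measures model starts with a step that cannot restore convergence and then drops straight to a single variance for all visits

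*SAP*

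**What the plan says.** SAP 5.4.6 analyses change from baseline in log(hsCRP) with a mixed model for repeated measures. On the covariance it says: "An unstructured covariance structure will be assumed for this model". The degrees-of-freedom method is Kenward-Roger.

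The contingency rule begins: "In case the MMRM model does not converge the following sequential steps will be used". Step 1 is to "change ddfm=kr to ddfm=bw. If still no convergence, perform step 2". Step 2 is to "change type=un to type=cs". The section names no intermediate covariance structure, no change of optimiser, starting values or iteration limit, and no empirical standard error.

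The code reads: "model CHG=TRT AVISITN WEIGHT BASE / s ddfm=kr; lsmeans TRT*AVISITN / diff cl". It therefore asks for treatment differences with intervals at each visit, although MODEL contains no treatment-by-visit term. Methotrexate use is in the section's text but not in its code.

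**The concern.** A pre-specified fallback should address the failure that triggers it and keep the requested output valid. Here the first step changes something applied only after the covariance parameters have been estimated. The second goes from a separate variance at each visit to one variance and one correlation for all visits.

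At stake is the calibration of the hsCRP intervals by visit, including Week 16, the last visit of the placebo-controlled period. Once the rule has been followed as written, the report would contain nothing to show that those intervals rest on a constant-variance assumption that was never checked.

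**Working it through.** The documents state no figure for this model, so there is none to reproduce.

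**Inputs from the documents**
- Arms: "100 secukinumab 300 mg, 100 secukinumab 150 mg and 50 placebo" (SAP 1.1).
- Level: "the default level of significance will be set to 0.05 (two-sided") (SAP 2.1), so 95% intervals.
- Visits: the row "High sensitivity C-Reactive protein (hsCRP") in Protocol Table 6-1 gives Weeks 1, 4, 8, 12 and 16, then every four weeks to Week 52. That is 5 post-baseline visits to Week 16 and 14 in all.
- SD of change in log(hsCRP) by visit: not given. All SDs below are assumptions.

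**Step 1.** The REML criterion is a function of the covariance parameters, the data and the fixed-effects design. It has no degrees-of-freedom term. Kenward-Roger and between-within are computed from the fitted covariance, so both need the same unstructured fit. If that fit fails to converge under one, it fails under the other. This needs no assumed data.

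**Number of covariance parameters for V visits**

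| Structure | Formula | V = 5 | V = 14 |
|---|---|---|---|
| Unstructured | V(V+1)/2 | 15 | 105 |
| Heterogeneous Toeplitz | 2V−1 | 9 | 27 |
| Heterogeneous AR(1) or CS | V+1 | 6 | 15 |
| Compound symmetry | 2 | 2 | 2 |

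The plan moves from the first row to the last and skips those between.

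**Step 2.** Take complete data, treatment-by-visit means and the same covariance in each arm. The compound-symmetry variance then estimates the mean of the visit variances v₁…v_V. At visit j:

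- SE ratio (model/true) = √(mean(v)/v_j)
- type I error = 2·[1 − Φ(1.96 × SE ratio)]

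Worked case, SDs 0.70, 0.7875, 0.875, 0.9625, 1.05 over the five visits:
- variances 0.4900, 0.6202, 0.7656, 0.9264, 1.1025; mean 0.7809; square root 0.8837
- Week 16: 0.8837/1.05 = 0.842, so the SE is 16% too small; type I error 9.9%
- Week 1: 0.8837/0.70 = 1.262, so the SE is 26% too large; type I error 1.3%

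| Assumed SDs, Weeks 1, 4, 8, 12, 16 | Week 16 SE | Week 16 type I error | Week 1 SE | Week 1 type I error |
|---|---|---|---|---|
| Equal | correct | 5.0% | correct | 5.0% |
| 0.85 to 1.00, equal steps | 7% too small | 6.9% | 9% too large | 3.3% |
| 0.70 to 1.05, equal steps | 16% too small | 9.9% | 26% too large | 1.3% |
| 0.60 to 1.10, equal steps | 21% too small | 12.2% | 45% too large | 0.5% |
| 0.85, 0.91, 0.95, 0.98, 1.00 | 6% too small | 6.6% | 11% too large | 3.0% |
| 0.70, 0.85, 0.93, 1.00, 1.05 | 13% too small | 8.8% | 31% too large | 1.1% |
| 0.60, 0.80, 0.95, 1.03, 1.10 | 17% too small | 10.4% | 52% too large | 0.3% |

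The end-to-end SD ratios are 1.00/0.85 = 1.18, 1.05/0.70 = 1.50 and 1.10/0.60 = 1.83. The last three rows put more of the rise early, which shows that the size depends on the path as well as the end points.

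**Simulation check.** This used 4,000 trials per scenario, arms of 100/100/50, five visits, within-patient correlation 0.6, complete data and SDs rising in equal steps. For last-to-first SD ratios of 1, 1.25, 1.5 and 2, last-visit coverage of the 300 mg versus placebo 95% interval under compound symmetry was 95.0%, 92.5%, 89.0% and 86.5%. The formula gives 95.0%, 92.3%, 90.1% and 86.9%. With a separate variance per visit, coverage was 94.1% to 95.5% at every visit in all four scenarios.

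**The model as coded.** With treatment as a main effect only, complete data give a contrast of visit averages. Its variance is proportional to the sum of all entries of the covariance matrix divided by V². Compound symmetry fits the mean variance s² and the mean covariance c, which gives (s² + (V−1)c)/V, the same quantity. So the main-effect contrast is not distorted. The error above arises only once visit-level contrasts can be estimated.

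**The case against.** **Step 1 is harmless.** If it cannot rescue the fit, the plan moves on and nothing is reported from it. This largely stands. The step is wasted rather than damaging, and losing the small-sample correction matters little with about 250 patients. Between-within might also avoid a computing burden after the fit, but that is not the stated trigger.

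**The fallback may never be used.** A reader might infer from the 14 scheduled visits that 105 parameters make non-convergence likely. The documents do not support that. SAP 5.4.6 is an appendix of model code that sets no last visit. Section 2.13 is absent from the public text and may define the analysis. SAP 2.1 focuses placebo comparisons on the first 16 weeks, where 15 parameters for about 250 patients is no obvious difficulty.

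**The intervals need not be wrong.** A reader might also infer that compound symmetry makes them wrong in every case, too wide early and too narrow late. That requires variances that rise over time. The documents report none, and with equal variances the coverage is nominal.

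**The code cannot produce these intervals anyway.** LSMEANS requests a treatment-by-visit effect that MODEL omits. This stands and is the more basic defect. The fallback matters only once it is repaired, so the two changes belong together.

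**Low consequence.** log(hsCRP) is neither the primary variable nor among the 12 secondary variables in SAP 2.7.1. This stands and sets the priority.

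**Conclusion.** The fallback is poorly ordered. That step 1 cannot cure non-convergence, and that step 2 removes visit-specific variances without a robust standard error, follows from the methods themselves and needs no assumed data.

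The effect on results is conditional on three things: the unstructured fit fails, the visit variances differ, and the MODEL line has been corrected to allow visit-level contrasts. Under SDs rising by a ratio of about 1.2 to 1.8 with complete data, the Week 16 standard error would be roughly 6% to 21% too small and the type I error about 6.5% to 12%, with the opposite error at Week 1. With equal SDs it is zero. Missing data, which would make the assumed correlation matter too, are not covered by these figures.

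This is a minor, inexpensive improvement to an analysis outside the listed primary and secondary variables. It has no bearing on the ACR20 result.

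**What to change.** Replace the two steps in SAP 5.4.6 with:

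1. Keep `type=un` and change the optimisation: Fisher scoring, starting values, iteration limit.
2. If it still fails, fit heterogeneous Toeplitz, then heterogeneous AR(1), then heterogeneous compound symmetry, and take the first that converges. Use the empirical (sandwich) covariance with a compatible degrees-of-freedom method such as between-within. Kenward-Roger corrects the model-based covariance, so it should not be paired with the sandwich.
3. Delete the change of degrees-of-freedom method as a convergence step. Between-within then appears only as the companion to the sandwich in item 2.

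In the same edit, add `TRT*AVISITN` and methotrexate use to the MODEL line (with methotrexate in CLASS), name the interaction in the text, and state the last visit modelled if Section 2.13 does not already do so.

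The cost is a few lines of SAP text and code and slightly more programming. The drawback is that sandwich standard errors are somewhat less stable with about 50 placebo patients.

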5.5 Rule of exclusion criteria of analysis sets

Table 5.5-1	Protocol deviations that cause subjects to be excluded
-------------	--

Protocol deviation ID	Deviation text description	Severity code	Excluded from analysis set
INCL01	Patients have not signed Informed Consent Form prior to initiation of any study related procedure.	1	Exclude from Full Analysis Set and Safety Set
INCL02A	Age criteria not met.	1	Include in everything
INCL02B	Non-pregnant, Non-lactating female patients.	1	Include in everything
INCL03A	Diagnosis of PsA classified by CASPAR criteria and with symptoms for at least 6 months with moderate to severe PsA who must have had at Baseline \geq 3 tender joints out of 78 and \geq 3 swollen joints out of 76 (dactylitis of a digit counts as one joint each).	1	Include in everything
INCL03B	Diagnosis of PsA classified by CASPAR criteria and with symptoms for at least 6 months with moderate to severe PsA who must have had Diagnosis of PsA classified by CASPAR criteria and with symptoms for at least 6 months with moderate to severe PsA who must have had at Baseline < 3 tender joints out of 78 and \geq 3 swollen joints out of 76 (dactylitis of a digit counts as one joint each)	1	Include in everything

INCL03C	Diagnosis of PsA classified by CASPAR criteria and with symptoms for less than 6 months with moderate to severe PsA who must have had Diagnosis of PsA classified by CASPAR criteria and with symptoms for at least 6 months with moderate to severe PsA who must have had at Baseline ≥ 3 tender joints out of 78 and < 3 swollen joints out of 76 (dactylitis of a digit counts as one joint each)	1	Include in everything
INCL03D	Diagnosis of PsA classified by CASPAR criteria and with symptoms for less than 6 months with moderate to severe PsA who must have had Diagnosis of PsA classified by CASPAR criteria and with symptoms for at least 6 months with moderate to severe PsA who must have had at Baseline < 3 tender joints out of 78 and < 3 swollen joints out of 76 (dactylitis of a digit counts as one joint each)	1	Include in everything
INCL04	Subject's target psoriatic skin lesion with a PASI score should be 1 or greater will be included in the study	1	Include in everything
INCL05	RF and/or Anti-cyclic citrullinated peptide (anti-CCP) antibodies should be negative at screening.	1	Include in everything
INCL06	Patients regularly using NSAIDs, as part of their PsA therapy should be on stable dose for at least 2 weeks before randomization to allow inclusion. And, they should remain on a stable dose in the study up to Week 16.	1	Include in everything
INCL07A	Patients taking corticosteroids are on a stable dose of less than or equal to 10mg per day prednisone or equivalent for at least 2W before randomization and should remain on a stable dose up to week 16.	1	Include in everything
INCL07B	Patients taking corticosteroids are on a stable dose of less than or equal to 10mg per day prednisone or equivalent for at least 2W before randomization and should remain on a stable dose up to week 16.	1	Include in everything
INCL08	Patients taking MTX (≤ 25 mg/week) are allowed to continue their medication if the dose is stable for at least 4 weeks before	1	Include in everything

	randomization and must remain on a stable dose up to study completion		
INCL09	Patients on MTX must be on stable folic acid supplementation at randomization	1	Include in everything
INCL10	Patients who are on a DMARD other than MTX must discontinue the DMARD 4 weeks prior to randomization, except for leflunomide, which has to be discontinued for 8 weeks prior to randomization unless a cholestyramine washout has been performed.	1	Include in everything
EXCL01	Subjects with Chest X-ray or MRI with evidence of ongoing infectious or malignant process, obtained within 3 months prior to screening and evaluated by a qualified physician should not be included in the study.	1	Include in everything
EXCL02	Subjects with previous exposure to Secukinumab or any other biologic drug directly targeting IL-17 or IL-17 receptor should not be included in the study	1	Include in everything
EXCL03	Subjects in use of any investigational drug and/or devices within 4 weeks before randomization, or a period of 5 half-lives of the investigational drug, whichever is longer should be excluded from the study	1	Include in everything
EXCL04	 Ongoing use of prohibited psoriasis treatments / medications (e.g., topical corticosteroids, UV therapy) at randomization OR Insufficient washout of prohibited psoriasis treatments: Oral or topical retinoid are excluded 4 weeks prior to randomization Photochemotherapy (e.g. PUVA) is excluded 4 weeks prior to randomization Photoherapy (e.g. UVA or UVB) is excluded 2 weeks prior to randomization Topical skin treatments (except in face, eyes, scalp and genital area during screening, only corticosteroids with mild to moderate potency) is are excluded 2 weeks prior to 	1	Include in everything

EXCL05	Subjects with history of hypersensitivity to the study drug or its excipients or to drugs of similar chemical classes should not be included in the study.	1	Include in everything
EXCL06	Subjects with any intramuscular or intravenous corticosteroid treatment within 4 weeks before randomization should not be included in the study	1	Include in everything
EXCL07	Subjects with intra-articular injections therapy (e.g. corticosteroid) within 4 weeks before randomization should not be included in the study.	1	Include in everything
EXCL08	Patients who ever received biological immunomodulating agents those targeting TNF alpha, IL6 and IL12/ IL23 investigational or approved should not be included in the study	1	Include in everything
EXCL09	Patients with previous treatment with any cell-depleting therapies including but not limited to anti-CD20, investigational agents (e.g.,alemtuzumab, anti-CD4, anti-CD5, anti-CD3, anti-CD19) should not be included in the study.	1	Include in everything
EXCL10	Subjects ,who are pregnant or nursing (lactating) women, where pregnancy is defined as the state of a female after conception and until the termination of gestation, confirmed by a positive human chorionic gonadotropin (hCG) laboratory test should not be included in the study.	1	Include in everything
EXCL11	 Women of child-bearing potential, defined as all women physiologically capable of becoming pregnant, unless they are using effective methods of contraception during entire study or longer if required by locally approved prescribing information. Effective contraception methods include: Total abstinence, when this is in line with the preferred and usual lifestyle of the patient. Periodic abstinence (e.g., calendar, ovulation, symptothermal, post-ovulation methods) and withdrawal are not acceptable methods of contraception 	1	Include in everything

	 Female sterilization (have had surgical bilateral oophorectomy with or without hysterectomy) or tubal ligation at least six weeks before taking study treatment. In case of oophorectomy alone, only when the reproductive status of the woman has been confirmed by follow up hormone level assessment Male sterilization (at least 6 months prior to screening). For female patients on the study, the vasectomized male partner should be the only partner for that patients 		
	 Barrier methods of contraception: Condom or Occlusive cap (diaphragm or cervical/vault caps) with spermicidal foam/gel/film/cream/vaginal suppository Use of oral_injected or implanted hormonal 		
	methods of contraception or other forms of hormonal contraception that have comparable efficacy (failure rate <1%), for example hormone vaginal ring or transdermal hormone contraception		
	 Placement of an intrauterine device or intrauterine system In case of use of oral contraception, women should have been stable on the same pill for a minimum of 3 months before taking study 		
	treatment. Women are considered post-menopausal and not of child bearing potential if they have had 12 months of natural (spontaneous) amenorrhea with an appropriate clinical profile (e.g., age appropriate, history of vasomotor symptoms) or six months of spontaneous amenorrhea as defined by		
	Central Lab FSH and/or estradiol levels		
EXCL12	Subjects with active ongoing inflammatory diseases other than PsA that might confound the evaluation of the benefit of Secukinumab therapy, should not be included in the study.	1	Include in everything
EXCL13	Subjects with underlying metabolic, hematologic, renal, hepatic, pulmonary, neurologic, endocrine, cardiac, infectious or	1	Include in everything

	gastrointestinal conditions, which in the opinion of the investigator immunocompromises the patient and/or places the patient at unacceptable risk for participation in an immunomodulatory therapy should not be included in the study.		
EXCL14	Subjects with significant medical problems or diseases, including but not limited to the following: uncontrolled hypertension (≥ 160/95 mmHg), congestive heart failure (New York Heart Association status of class III or IV), uncontrolled diabetes, should be excluded from the study.	1	Include in everything
EXCL15	Subjects with the history of clinically significant liver disease or liver injury as indicated by abnormal liver function tests such as SGOT (AST), SGPT (ALT), alkaline phosphatase, or serum bilirubin should not be included in the study.	1	Include in everything
EXCL16	Subjects with the history of renal trauma, glomerulonephritis, or patients with one kidney only, or a serum creatinine level exceeding 1.5 mg/dL (132.6 µmol/L) should not be included in the study.	1	Include in everything
EXCL17	Subjects with total WBC count $<3,000/\mu$ L, or platelets $<100,000/\mu$ L or neutrophils $<1,500/\mu$ L or hemoglobin <8.5 g/dL (85 g/L) at screening should not be included in the study.	1	Include in everything
EXCL18	Subjects with active systemic infections during the last two weeks prior to randomization (exception: common cold) should be excluded from the study.	1	Include in everything
EXCL19A	Subjects with the history of ongoing, chronic or recurrent infectious disease or evidence of tuberculosis infection as defined by either a positive purified protein derivative (PPD) skin test (the size of induration will be measured after 48-72 hours, and a positive result is defined as an induration of \geq 5 mm or according to local practice/guidelines) or a positive QuantiFERON TB-Gold test as indicated in the assessment schedule	1	Include in everything

EXCL19B	No history of ongoing, chronic or recurrent infectious disease or evidence of tuberculosis infection as defined by either a positive purified protein derivative (PPD) skin test (the size of induration will be measured after 48-72 hours, and a positive result is defined as an induration of \geq 5 mm or according to local practice/guidelines) or a positive QuantiFERON TB-Gold test as indicated in the assessment schedule	1	Include in everything
EXCL20	Subject with Known infection with human immunodeficiency virus (HIV) or human immunodeficiency virus , hepatitis B or hepatitis C at screening or randomization should be excluded from the study.	1	Include in everything
EXCL21	Subjects with the history of lymphoproliferative disease or any known malignancy or history of malignancy of any organ system within the past 5 years should not be included in the study (except for basal cell carcinoma or actinic keratoses that have been treated with no evidence of recurrence in the past 3 months, carcinoma in situ of the cervix or non- invasive malignant colon polyps that have been removed)	1	Include in everything
EXCL22	Subjects with current severe progressive or uncontrolled disease which in the judgment of the clinical investigator renders the patient unsuitable for the trial.	1	Include in everything
EXCL23	Subject's inability or unwillingness to undergo repeated venipuncture (e.g., because of poor tolerability or lack of access to veins) should not be included in the study.	1	Include in everything
EXCL24	Subject with any medical or psychiatric condition which, in the Investigator's opinion, would preclude the participant from adhering to the protocol or completing the study per protocol should not be included in the study	1	Include in everything
EXCL25	Subject donation or subject with loss of 400 mL or more of blood within 8 weeks before	1	Include in everything

	dosing (randomization) should not be included in the study		
EXCL26	Subjects with the history or evidence of ongoing alcohol or drug abuse, within the last six months before randomization should not be included in the study	1	Include in everything
EXCL27	Subjects who have plans for administration of live vaccines during the study period or 6 weeks prior to randomization should not be included in the study	1	Include in everything
TRT01	Incorrect study medication administered by subject	4	Include in everything
TRT02	Any incorrect route of administration of study drug used at any time during the study, per protocol	4	Include in everything
TRT03	Two records with same "Date of dose" (i.e., Injection A and B)	4	Include in everything
TRT04	At Weeks 16, 28 and 40 patients on secukinumab 150 mg (Group 2) who are responders will continue to receive secukinumab 150 mg (1.0 mL) plus placebo (1.0 mL) every 4 weeks until next evaluation of responder status at weeks 28 or 40.	4	Include in everything
TRT05	Patients who did not meet the responder criteria at Week 16, 28 or 40 will start receiving secukinumab 300 mg s.c.every 4 weeks and will continue this dose up to Week 52.	4	Include in everything
TRT06	Missed or partial doses of study medication administered by subject	4	Include in everything
COMD01	Use of prohibited medication at any time during the study after randomization until Week 16	5	Include in everything
COMD02	Use of prohibited medication with potential impact on key efficacy and/or safety evaluations at any time during the study after Week 16	5	Include in everything
COMD03	subject received a live virus vaccination during the study	5	Include in everything
OTH01	If Date of visit is recorded then the Physician's Global Assessment QSRSFLT at corresponding visits are not expected to be null.	998	Include in everything

Novartis
SAP

OTH02	PASI score is blank when visit date is present and PASI total score is missing.	998	Include in everything
OTH03	If the sex of the subject is Female and the response to "Is subject of child bearing status" is recorded as "Able to bear children" on Demography CRF then the "Date of assessment" Urine pregnancy test CRF is not expected to null at Visits Baseline, Week 4, Week 12, Week 16, Week 32, Week 24, Week 40	998	Include in everything
OTH04	What was the result of the tuberculosis workup? = "Latent" then on prior conmed page, medication with reason 'tuberculosis' (% preferred term) is present with start date prior to <date assessment="" of=""> on tuberculosis assessment page. If false, then Screening disposition page 2 with subject status as Screen Failure should appear.</date>	998	Include in everything
OTH05	Screening and Baseline visits occurred on the same date so eligibility could not be confirmed at time of randomization	998	
OTH06	ICH-GCP non-compliance of study site in the study	998	
OTH07	Failure to perform key study procedures	998	

6 References

- Garwood, F (1936). Fiducial limits for the Poisson distribution. Biometrika; 46: 441–453.
- Newcombe RG (1998) Two-sided confidence intervals for the single proportion: comparison of seven methods. Statistics in Medicine; 17: 857-872.
- Sahai H, Khurshid Anwer (1993) Confidence intervals for the mean of a poisson distribution: a review. Biom J, 35 (7): 857-867.

• Ulm K (1990) A simple method to calculate the confidence interval of a standard mortality ratio. American Journal of Epidemiology, 131(2): 373-375.
